2.3.2 Secondary objectives

- 1. To assess participants response (treatment efficacy) to varying dose concentrations, dose frequency, length of treatment, and formulation of *Artemisia afra* treatment.
- 2. To identify the most acceptable dose concentration, dose frequency, length of treatment, and formulation (flavor) of Artemisia treatment.
- 3. To assess the safety (ASE) of *Artemisia afra* treatment in participants by dose concentration, dose frequency, length of treatment, and formulation. As a commonly used tea, no toxicity is expected.
- 4. To assess variability of plasmodium test predictive values between mRDT, rtPCR, and direct blood smear observation in asymptomatic persons.

Treatment outcomes

Major outcome

• Decrease in parasite load over time.

Secondary outcomes

- Decrease in gametocyte load in carriers with Artemisia afra tea by dose concentration, dose frequency, length of treatment, and formulation.
- Acceptability (adherence and completion) of *Artemisia afra* treatment by dose concentration, dose frequency, length of treatment, and formulation (flavor).

- Safety (SAEs) of *Artemisia afra* treatment in participants by dose concentration, dose frequency length of treatment, and treatment formulation.
- Absolute increase in Cycle threshold (Ct >20).
- Likelihood and variability in the rate of reservoir elimination with treatment, compliance/ acceptability, and occurrence of side effects /adverse events in different treatment arms.

Treatment endpoints

Primary endpoints

• Proportion of people with decreased gametocyte load after treatment with *Artemisia afra* tea on Day 35 from baseline.

Secondary endpoints

- Level of decrease in gametocyte load (rt-PCR Ct) in the different treatment arms at D7, D14, D28, and D35 from baseline (activity level and optimal dosage schedule).
- Level of decrease in gametocyte load the various treatment arms (rt-PCR Ct) by gender, age, and trial entry parasite load, at D7, D14, D28, and D35 from baseline.
- Absolute increase in Cycle threshold (Ct >20) in various treatment arms at D7, D14, D28, and D35 from baseline.
- Proportion of people in the various treatment arms who respect and complete the prescribed treatment dosages (accepted dosage schedule and drug formulation).
- Proportion of persons on the various arms of treatment who develop clinical symptoms at D7, D14,
 D28, and D35 from baseline.

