- Proportion of people on the various arms of treatment who develop ASEs or AEs at D7, D14, D28, and D35 from baseline (No severe adverse side effects are expected).
- Proportion of persons on the various arms of treatment who withdraw from study due to severe ASEs or AEs at D7, D14, D28, and D35 from baseline.
- Proportion of persons on the various arms of treatment who withdraw from study for reasons other than severe AEs at D7, D14, D28, and D35 from baseline.
- Proportion of persons with baseline discordant test results (False positive or false negative) between mRDT, rt PCR, and direct blood smear observation?

Exploratory endpoints

- Variability in level of decease in gametocyte load (rt-PCR Ct) in the various treatment arms at D7, D14, D28, and D35 from baseline.
- Variability in level of decease in gametocyte load (rt-PCR Ct) in the various treatment arms by gender, age, and trial entry parasite load, at D7, D14, D28, and D35 from baseline.
- Variability in attainment of absolute increase in Cycle threshold (Ct >20) in the various treatment arms at D7, D14, D28, and D35 from baseline.

- Variability in the proportion of participant who respect and complete prescribed treatment dosages (acceptability) in the various treatment arms.
- Variability in the proportion of participants who develop clinical symptoms in the various treatment arms at D7, D14, D28, and D35 from baseline.
- Variability in the proportion of participants who develop Severe ASEs in the various treatment arms at D7, D14, D28, and D35 from baseline (not expected).
- Variability in proportion of participants who withdraw from the study due to severe ASEs, in the various treatment arms, at D7, D14, D28, and D35 from baseline.
- Variability in proportion of participants who withdraw from the study for reasons other than severe AEs, in the various arms of treatment at D7, D14, D28, and D35 from baseline.

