Clinical symptoms (mild malaria symptoms): That may occur during the trial period will be assessed daily by site (observing) staff and recorded in the home or site visit worksheets at Visit Day 7, 14,28, and 35 including Temperature > 37°C, Chills (Perspiration), Sweats, Headaches, nausea and vomiting, body aches, general malaise (Weakness), enlarged spleen, mild jaundice, enlargement of the liver, and increased respiratory rate (>20 /min). Participants with confirmed malaria symptoms will be treated with the WHO recommended treatment for symptomatic malaria.

Data collection: Data will be captured through the Observation worksheet and entered in Electronic Case Report Forms (eCRF), by interviewing the participants during observation, reviewing available medical records, and documenting assessment records.

Written informed consent will be obtained before conducting any study related procedures or treatment on the participants. Participants will first be informed about the aim of the study, designs, potential gain, and their right to stop at any moment if they accept to enter the study. Then they will be requested to sign a written informed consent.

Ethical considerations: Administrative authorization will be obtained from the ministry of public health in Cameroon and Rwanda, and administrative authorities of the various study sites. Ethical authorization will be obtained from the Faculty of Health science Institutional Review Board (FHSIRB) of the University of Buea, Cameroon and the Rwandan National Ethical Committee (RNEC). All study participants will have a clear and detailed explanations about the study and requested to freely sign a written informed consent.

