4. STUDY POPULATION

The study will be conducted at the University of Buea in Cameroon, and the University of Rwanda. All students and staff members of the University will be invited to participate. In the University of Buea, there are about 12,000 students and 973 staff members (500 teachers and 473 administrative /supporting staff. The University of Rwanda (UR) has about 30,445 students and 2,266 staff members (1450 teachers and 816 administrative /supporting). All students and staff members of the University will be invited to participate in the study. Participants will be included in the study if in good health as judged by physical examination and medical history, and if they meet all specified eligibility criteria.

Table 3: Inclusion and exclusion criteria.

Inc	Inclusion criteria for trial allocation groups		Exclusion criteria for trial allocation groups	
1.	Be student or worker of a participating	1. To have a known hypersensitivity to any ingredients		
	University.		of the tea.	
2.	Be 18 years and above, and in good general	2.	Currently taking a malaria drug for prevention or	
	health condition.		treatment.	
3.	Have a device (phone, tablet, etc) that will	3.	To have participated in another malaria drug trial or	
	support remote visits.		device in the last 14days.	
4.	Sign written informed consent form.	4.	To have a history or presence of clinically significant	
5.	Screened positive for malaria (RDT + and		medical, psychiatric, or emotional condition.	
	qPCR +) but asymptomatic.	5.	Reported diabetic.	

5-STUDY PROCEDURES

5.1 General considerations: The study will be conducted in accordance with the ethical principles for medical research involving humans in the World medical associations declaration of Helsinki (36). The study will be initiated only after approvals from relevant authorities, ethical and institutional review boards have been obtained. Freely given and written informed consent must be obtained from each participant prior to participation in the study.

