7.2 Safety Laboratory Measurements

This study has no safety laboratory measurements.

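### The clinical-symptoms endpoint can count normal temperatures, and it lacks an item-level Day 0 record and a rule for its overlap with adverse events

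*Protocol*

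**What the plan says.** Section 3 (Clinical symptoms) defines the symptoms by a list: "including Temperature > 37°C, Chills (Perspiration), Sweats, Headaches, nausea and vomiting, body aches, general malaise (Weakness), enlarged spleen, mild jaundice, enlargement of the liver", ending with "increased respiratory rate (>20 /min". They "will be assessed daily by site (observing) staff and recorded in the home or site visit worksheets at Visit Day 7, 14,28, and 35". The list states no minimum number of items, no repeat reading and no site of temperature measurement.

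The list feeds a secondary endpoint in section 2 (Treatment endpoints): "Proportion of persons on the various arms of treatment who develop clinical symptoms at D7, D14", continuing to Days 28 and 35 from baseline. An exploratory endpoint looks at how the same proportion varies by arm. A separate secondary endpoint in the same section reads "Proportion of people on the various arms of treatment who develop ASEs or AEs".

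At entry, Table 3 in section 4 asks for general good health and a positive RDT and "qPCR +) but asymptomatic". Day 0 includes a medical history and a physical assessment, with no items named. In Table 4 (section 5.6) the line for occurrence of clinical symptoms stands under Days 7, 14, 28 and 35, and not under Day 0.

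**The concern.** An endpoint that counts what participants develop from baseline needs the same items observed at baseline. Here the list starts at Day 7. A carrier who enters at 37.2°C or with a palpable spleen could be accepted as asymptomatic, because nothing ties that word to the list. With no change at all, the same finding could be ticked at Day 7. Because temperature above 37°C is on the list, some well participants would be ticked by ordinary variation.

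The second issue is where a listed symptom is reported. Headache, nausea, malaise or jaundice after dosing could be an effect of the tea, a sign of malaria or neither. The list is headed as mild malaria symptoms and reported apart from side effects and AEs, with no statement of how the two records relate. Section 7.2 states that "This study has no safety laboratory measurements", so jaundice and liver enlargement are among the few hepatic signs this trial could observe. How they reach the safety tables should not be left to each observer.

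**Working it through.** **No planned figure to reproduce.** The protocol gives no expected rate, power or sample size for this endpoint. Arm sizes are 8 (active) and 4 (control) per site, so 16 and 8 over two sites; 6 × 8 + 2 × 4 = 56 per site and 112 in all, as stated.

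**Step 1: normal readings above 37°C.** The protocol gives no temperature distribution. Assume temperature in well adults is normal with mean m of 36.4 to 36.8°C and SD s of 0.3 to 0.4°C, and that this one item is enough to count a participant. Then p = 1 − Φ((37.0 − m)/s). For four independent visit readings, P(at least one) = 1 − (1 − p)^4. The last column is a simulation of 200,000 persons with within-person correlation 0.5.

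| m | s | z | One reading | Any of 4, independent | Any of 4, correlation 0.5 |
|---|---|---|---|---|---|
| 36.4 | 0.3 | 2.00 | 2.3% | 8.8% | 7.0% |
| 36.4 | 0.4 | 1.50 | 6.7% | 24.2% | 18.5% |
| 36.6 | 0.3 | 1.33 | 9.1% | 31.8% | 24.1% |
| 36.6 | 0.4 | 1.00 | 15.9% | 49.9% | 37.4% |
| 36.8 | 0.3 | 0.67 | 25.2% | 68.8% | 52.5% |
| 36.8 | 0.4 | 0.50 | 30.9% | 77.1% | 60.1% |

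In an active arm of 16, one visit flags 16 × 0.0228 = 0.4 to 16 × 0.3085 = 4.9 well participants. Over four visits it is 16 × 0.070 = 1.1 to 16 × 0.601 = 9.6 with correlation 0.5, or up to 16 × 0.771 = 12.3 if readings are independent. Any daily checks that include a temperature, and the ten other items, can only add to this.

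**Step 2: effect on the comparison.** Let f be the false-flag probability, the same in every arm and independent of true symptoms, and q the true proportion. The observed proportion is f + (1 − f)q, so a true difference between arms shrinks by the factor (1 − f). At one visit the factor is 1 − 0.0228 = 0.98 to 1 − 0.3085 = 0.69. Over four visits with correlation 0.5 it is 1 − 0.070 = 0.93 to 1 − 0.601 = 0.40.

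**Step 3: the baseline.** The endpoint is defined as change from baseline. Table 4 schedules the items at each follow-up visit and not at Day 0, and the Day 0 assessment is not itemised. Item-by-item subtraction therefore relies on whatever the examiner happened to write down.

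**Step 4: overlap with AEs.** Section 7.1 defines side effects and AEs broadly and gives no item list. A post-dose headache can satisfy the section 3 list and also either definition in 7.1. Severity grading and relatedness (7.1), and the separate handling of pre-treatment events (7.1.2), are specified for AEs and not for the symptom list. The synopsis merges symptoms, side effects and AEs in one secondary endpoint; section 2 reports symptoms separately from side effects and AEs. No text reconciles the two.

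**The case against.** The strongest reply is that Day 0 is not empty. It has a history and a physical assessment, entrants must be asymptomatic and in good health, and the endpoint wording points to new findings only. That stands. A reader might infer that there is no baseline at all, or that unchanged findings are counted by rule; the protocol says neither. What remains is that the items needed to apply the wording are not scheduled at Day 0. A later analysis plan could supply a case rule, but it cannot recover Day 0 items that were never recorded.

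A reader might also infer that a drug effect will be booked as malaria and escape the safety assessment or the pause rule in 7.4. The text does not support this. The AE definition is broad and excludes none of the listed symptoms, 7.1 allows an event to be related even when other causes could explain it, and the pause rule needs a treatment-related Grade 4 AE or SAE. Nor does the list share items with a side-effect list, since none exists. The overlap is by definition, and the gap is a missing assignment rule.

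Finally, it is tempting to say that false positives swamp the endpoint. That depends on the assumed temperatures and on one item sufficing; at 2% per reading nothing is swamped. The temperature item acts in all arms alike, so by itself it does not favour one arm. Section 6.2 assigns one observer to each arm, so differences between raters on subjective items could coincide with arm, but the documents do not show that this would happen.

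**Conclusion.** The point holds in a limited form. As written, the symptom endpoint can count normal temperatures, cannot reliably exclude pre-existing signs item by item, and has no stated relation to AEs; the synopsis and section 2 also disagree on whether symptoms and AEs are pooled. The illustrative false-flag rate from temperature alone is 2% to 31% per reading and 7% to 60% over four visits with within-person correlation 0.5. These figures rest on an assumed temperature distribution and on a single item being enough to count. The direction does not change across that range; the size does. The consequence is mainly inflated and diluted proportions in a secondary and an exploratory endpoint of a pilot trial. The primary endpoint, based on gametocyte load, is untouched. The change should be made because it is nearly free before enrolment, and the Day 0 items cannot be recovered afterwards.

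**What to change.** 1. Add the section 3 items to the Day 0 row of Table 4, on the same worksheet as the follow-up visits, and count for the endpoint only items that were absent or less severe at Day 0.
2. Enter each listed item that appears or worsens after dosing in the AE record with severity and relatedness, and derive the symptom endpoint from that record. Jaundice and liver enlargement then always reach the safety tables.
3. Align the synopsis endpoint with section 2.
4. The sponsor should justify the temperature criterion used for the endpoint or reconcile it with the AE grading table adopted in 7.1. The sponsor should also reconcile how the list relates to the entry criterion and to the treatment instruction that follows it in section 3. No clinical threshold or treatment rule is proposed here.

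The unmodified list should not simply become the entry definition of asymptomatic. Buea expects 635 × 0.098 = 62.2 positives for 56 places. If carriers' temperatures followed the assumed distribution, removing 2.28% to 30.85% would leave 62.2 × 0.9772 = 60.8 to 62.2 × 0.6915 = 43.0, before the 10% drop-out.

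Cost: protocol and worksheet wording, a slightly longer Day 0 worksheet, more AE entries and fewer counted symptom events.

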4. STUDY POPULATION

The study will be conducted at the University of Buea in Cameroon, and the University of Rwanda. All students and staff members of the University will be invited to participate. In the University of Buea, there are about 12,000 students and 973 staff members (500 teachers and 473 administrative /supporting staff. The University of Rwanda (UR) has about 30,445 students and 2,266 staff members (1450 teachers and 816 administrative /supporting). All students and staff members of the University will be invited to participate in the study. Participants will be included in the study if in good health as judged by physical examination and medical history, and if they meet all specified eligibility criteria.

Table 3: Inclusion and exclusion criteria.

Inc	Inclusion criteria for trial allocation groups		Exclusion criteria for trial allocation groups	
1.	Be student or worker of a participating	1. To have a known hypersensitivity to any ingredients		
	University.		of the tea.	
2.	Be 18 years and above, and in good general	2.	Currently taking a malaria drug for prevention or	
	health condition.		treatment.	
3.	Have a device (phone, tablet, etc) that will	3.	To have participated in another malaria drug trial or	
	support remote visits.		device in the last 14days.	
4.	Sign written informed consent form.	4.	To have a history or presence of clinically significant	
5.	Screened positive for malaria (RDT + and		medical, psychiatric, or emotional condition.	
	qPCR +) but asymptomatic.	5.	Reported diabetic.	

5-STUDY PROCEDURES

5.1 General considerations: The study will be conducted in accordance with the ethical principles for medical research involving humans in the World medical associations declaration of Helsinki (36). The study will be initiated only after approvals from relevant authorities, ethical and institutional review boards have been obtained. Freely given and written informed consent must be obtained from each participant prior to participation in the study.

5.2 Community permission

After obtaining ethical and regulatory approvals, meetings will be held with representatives of participating University communities following specific site procedures, during which the study will be explained in detail (including the objectives, procedures, and implications to the participants) and the study team will answer any questions and concerns raised. The community leaders would review the information and confirm their permission for the conduct of the study. A communique for the study will then be put up in collaboration with the communication department of each University, bearing the precise study period and a reference contact for further clarifications.

5.3 Recruitment: During the baseline visit at the site health stations on Day 0, informed individuals will be invited to participate in a screening and cohort survey on asymptomatic malaria. After informed

consent is obtained, baseline assessments will be carried out and information obtained on participant's sociodemographic characteristics, clinical/medical history, physical assessment, prior medications and contact details. This will be followed by malaria screening tests and participants who fulfil the inclusion criteria will be enrolled in study.

5.4 Informed Consent

"Informed consent" is the voluntary agreement of an individual to participate in the research. Consent will be given with free will of choice, and without inducement. The individual will have sufficient knowledge and understanding of the nature of the proposed research, the anticipated risks and potential benefits, and the requirements of the research, to be able to make an informed decision. Two original copies of the informed consent forms will be signed so that one copy will remains with the participant, and one will be kept at the site.

5.5 Randomization and Blinding Procedures

Randomization: After enrolment of eligible participants, a statistician will randomly assign them in the 8 study arms before treatment administration. The randomization method will be a permuted block randomization, with a block size of either 14 or 28 at random, and with a two-to-one allocation ratio for each active arm against two different control arms (2:2:2:2:2:2:1:1). The treatments will consist of *Artemisia afra* infusions for the 6 trial arms versus flavored placebo infusions and any desired regular tea for the 2 control arms.

Blinding: Neither the participants nor the site staff (investigators or observers) will know to which study arm the participants have been assigned.

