- **TG 8**: Group of 4 participants receiving regular tea placebo taken as desired, daily for 1 week (7 days) (Regular tea with no active molecule).

Randomization. The randomization method will be a permuted block randomization, with a block size of either 14 or 28 at random, and with a two-to-one allocation ratio for each active arm against two different control arms (2:2:2:2:2:1:1)

Blinding: Partial blind.

Data collection: Data will be captured through an observation worksheet and entered in Electronic Case Reporting Forms (eCRF).

Figure 2 and 3 show study design

[figure not shown]

Figure 2. Screening and recruitment of study participants.

[figure not shown]

Figure 3. Algorithm to find the activity level, optimal dosage, and accepted formulation of *Artemisia afra* in eliminating plasmodium reservoirs.

Blood sample schedule: Five blood samples (approximately 1mL each) will be collected at Visit 1 (Day 0), Visit 2 (Day 7), Visit 3 (Day 14), Visit 4 (day 28), and visit 5 (day 35).

Study visits/assessment schedules: Five visits at Day0, Day7, Day14, Day28 and Day35.

Clinical symptoms (mild malaria symptoms): Clinical symptoms that may occur during the trial period will be assessed daily by site (observing) staff and recorded in the home or site visit worksheets throughout the study period.

Adverse side effects (ASEs) and adverse events (AEs): ASEs are not expected. Participants will be assessed daily by site staff during site and home visits/calls, within the 35 days study period and any AEs will be recorded in the eCRF (case report form).

ASEs and AEs leading to withdrawal will also be collected throughout the study period, by interviewing participants during site and home visits, and by reviewing of available medical records.

Written informed consent will be obtained before conducting any study related procedures or treatment on the participants. Participants will first be informed about the aim of the study,

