3. METHODOLOGY

Study Design: The study is a Phase 2 randomized controlled, partial-blind, parallel group study in plasmodium infected *asymptomatic* adults 18 years and older, with 8 study arms. It will use the adapted Zelen design. The adapted Zelen design uses two steps in the consent process. In the first step, there is an informed consent from all participants for a cohort lifestyle study. After consent is obtained, baseline assessment and screening will be performed, and eligible participants randomly assigned to the different study arms. According to this consent, participants are randomized without knowledge about the detailed protocol. In the second step, only participants from the intervention group will receive the information about the intervention and the second consent will be obtained from them. The participants who will decline to participate to an intervention will continue in the cohort study, as the control group.

Duration of study: The study duration is 35 days (5 weeks) for each participant.

Treatment groups (TG):

TG 1: Group of 8 persons receiving *A. afra* infusions of 5g/1liter of water, 3drinks a day, daily for 1week (7 days) (current recommendation).

TG 2: Group of 8 persons receiving *A. afra* infusions of 5g/500ml of water, 2drinks a day, daily for 1week (7 days) (increase concentration and decrease dose frequency).

TG 3: Group of 8 persons receiving *A. afra* infusions,5g/1liter of water 3drinks a day, weekly for 4weeks (decrease dose frequency and increase length of treatment).

TG 4: Group of 8 persons receiving flavored *A. afra* infusions, 5g/1liter of water 3drinks a day, daily for1week (7 days) (current treatment with improved taste).

TG 5: Group of 8 persons flavored *A. afra* infusions, 5g/500ml of water 2drinks a day, daily for 1 week (7 days) (improved taste, increase concentration and decrease dose frequency).

- **TG 6:** Group of 8 persons receiving flavored *A. afra* infusions, 5g/1liter of water 3drinks a day, weekly for 4weeks (improved taste, decrease dose frequency and increase length of treatment);
- **TG 7**: Group of 4 persons receiving flavored placebo infusions, 5g/liter of water 3drinks a day, daily for 1week (7 days) (improved taste with no active molecule);
- **TG 8**: Group of 4 participants receiving regular tea placebo taken as desired, daily for 1 week (7 days) (Regular tea with no active molecule).

[figure not shown]

Figure 2. Screening and recruitment of study participants

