Randomization: Prior to treatment, eligible participants will be randomly assigned into the 8 study arms. The randomization method will be a permuted block randomization, with a block size of either 14 or 28 at random, and with a two-to-one allocation ratio for each active arm against two different control arms (2:2:2:2:2:1:1).

Blinding: The participants in the intervention arms will be aware of their assignment to an intervention group but unaware of the treatment assigned to them. The site staff (investigators or observers) will be

aware of assignments to one control arm (regular tea group), but unaware of assignments in the other treatment arms.

Visits/assessment schedules: A total of five study visits will be effected, being one baseline visit on Day 0, and four follow-up visits on Day 7, 14, 28 and 35, from baseline. During the baseline visit plasmodium tests targeting specific parts of the gametocyte genes will be done to determine the participants' initial (baseline) parasite load, and during subsequent visits, follow up control tests (rtPCR and blood smear) will be done, and the gametocyte load recorded, alongside assessments for clinical symptoms and adverse sides effects (if any).

Endpoints The efficacy of each of the treatment dosage schedule will be evaluated on day 7,14,28 and 35 from baseline, based on response to treatment or reservoir elimination rate. Response to treatment will be indicated by an absolute increase in Cycle threshold (Ct >20), or a negative rt-PCR tests results (Ct >40). If the patient misses the follow-up visit, compliance will be noted in the completion worksheet (filled out at end of study) and the parasite load and adverse side effects noted during the last visit considered. No severe side adverse effects are expected from the treatment but since toxicity is always a concern in clinical trials involving humans, participants will be observed for any severe ASEs and withdrawal noted throughout the study duration.

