6.2 Treatment administration

After randomization and allocation, clear education, and demonstrations on how to prepare and consume the treatment will be provided to participants by the site investigator based on their randomization codes. Participants on the trial treatment arms will receive either of the Artemisia infusions of various dosage schedules and formulations, and participants on the placebo arms will drink either a flavored inactive infusion or the regular tea. The participants will take the treatment or placebo orally, under the supervision of one of the investigators (Observers). 8 observers will be assigned to follow up and assist participants on the various treatment arms (1 observer per treatment arm). The observer will encourage compliance to treatment, observe for side effects/ adverse events, and take note of participant's comments/appreciation of the treatment dosages and formulation, throughout the study period. The Observer will also effect home visits to participants when necessary (in case of loss to follow-up and difficulty to contact participant on cell phone).

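### Section 5.5 claims full blinding that Section 3 contradicts, and since the only prepared placebo matches TG4 alone, staff can infer active treatment in the other five active arms (80 of 96 active participants)

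*Protocol*

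**What the plan says.** The protocol describes blinding in several places, and the descriptions differ.

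- Section 5.5 (Randomization and Blinding Procedures): "Neither the participants nor the site staff (investigators or observers) will know to which study arm the participants have been assigned".
- Section 3 (Methodology, Blinding), on participants: "The participants in the intervention arms will be aware of their assignment to an intervention group but unaware of the treatment assigned to them". On site staff: they will be "aware of assignments to one control arm (regular tea group), but unaware of assignments in the other treatment arms".
- Synopsis (Blinding): "Partial blind". The design statements in the synopsis and in Section 3 use the same label.
- Section 6.3 has trained blinded site staff manage supply, administration and observation.

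Section 3 describes the main control, TG7, as "Group of 4 persons receiving flavored placebo infusions, 5g/liter of water 3drinks a day", taken every day for one week. TG8 is the participant's own tea, drunk as wished. Section 6.1 lists no other placebo.

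On delivery, Section 6.2 says that "demonstrations on how to prepare and consume the treatment will be provided to participants by the site investigator based on their randomization codes". It also assigns eight observers, one to each arm, who follow intake, watch for side effects and note participants' comments.

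**The concern.** There are two separate problems.

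First, Section 5.5 is the operative procedure, and it claims more than Section 3 and the synopsis allow. The two cannot both be followed.

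Second, Section 3's more limited claim, that staff are unaware of every arm except regular tea, needs the active and placebo arms to look alike to the people who handle them. They do not. Where no placebo uses a given volume, number of drinks, schedule or flavour, a staff member who knows the arm list and sees that feature knows that the tea is active.

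This matters because the same staff produce the outcomes most sensitive to knowing the treatment. Observing staff assess clinical symptoms daily (Section 3, Clinical symptoms). The investigator grades adverse events and decides whether they are related to treatment (Section 7.1), and relatedness feeds the pause rule in Section 7.4. Symptoms, side effects, adverse events and withdrawals are secondary endpoints by arm. A report that took its blinding description from Section 5.5 would credit these comparisons with a protection that the design does not give.

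**Working it through.** **Sample size reproduced.** Section 8.1 gives 8 participants in each of 6 active arms and 4 in each of 2 control arms, per site. That is 6 × 8 + 2 × 4 = 56 per site, and 2 × 56 = 112 over two sites, as the protocol states. Over both sites there are 2 × 8 = 16 per active arm, 2 × 4 = 8 per control arm, and 6 × 16 = 96 active participants.

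**Each active arm against TG7**, from the treatment groups in Section 3:

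| Arm | Flavoured | Water volume | Drinks per day | Schedule | Differs from TG7 in |
|---|---|---|---|---|---|
| TG7 (placebo) | yes | 1 litre | 3 | daily, 1 week | (reference) |
| TG1 | no | 1 litre | 3 | daily, 1 week | flavour |
| TG2 | no | 500 ml | 2 | daily, 1 week | flavour, volume, drinks |
| TG3 | no | 1 litre | 3 | weekly, 4 weeks | flavour, schedule |
| TG4 | yes | 1 litre | 3 | daily, 1 week | nothing listed |
| TG5 | yes | 500 ml | 2 | daily, 1 week | volume, drinks |
| TG6 | yes | 1 litre | 3 | weekly, 4 weeks | schedule |

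Five arms have no matched placebo: 5 × 16 = 80, and 80/96 = 83%. The one nominally matched pair is TG4 (16) against TG7 (8).

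**How firm the inference is for staff.** In TG2, TG3, TG5 and TG6 (4 × 16 = 64 participants, 64/96 = 67%) the difference lies in volume, number of drinks or schedule. Section 6.2 has the site investigator demonstrate preparation and consumption, so these features cannot be hidden from that person. In TG1 (16 participants) the only difference is flavour, so the inference also needs the flavouring to be noticeable to staff during preparation, or through the comments on formulation that observers must record.

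**The matched pair.** With one observer per arm, everyone followed by the TG4 observer is on one treatment and everyone followed by the TG7 observer on another. The protocol does not say how the arm's identity would be kept from those observers. Nor does it say that the flavoured placebo was made to taste like flavoured *A. afra*. The match is therefore nominal.

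**Contrasts with TG8.** Section 3 itself says that staff know the regular-tea assignments, so no contrast with TG8 is assessor-blind, for any of the 96 active participants.

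**The case against.** The strongest reply is that the protocol's overall position is partial blinding. The synopsis and the Section 3 design statement say so, Section 3 spells out a limited version, and Section 5.5 is the outlier. That is fair, and it makes part of this a wording conflict. It does not rescue Section 3, whose limited version still claims that staff are unaware of seven of the eight arms.

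A reader might go further in four directions that the documents do not support.

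- *The comparisons are open to participants too.* A participant could deduce active treatment only by knowing which regimens the placebo uses. Under the adapted Zelen design, participants are randomised before they learn the details, and TG1 to TG7 all pass through a second consent whose content is not shown. Unmasking is possible but not established.
- *Acceptability is biased.* The stated objective is to find the most acceptable concentration, frequency, length and flavour. Perceiving these is the exposure under test, not a failure of masking.
- *The weekly arms have no safety control.* All arms are followed for adverse events to Day 35, so TG7 and TG8 give background rates over the same period. Only the intake pattern is unmatched.
- *Laboratory reading is exposed through the participant code.* Section 10.4 puts a serial registration number in the code, but nothing shows that it reveals the arm.

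Two further points stand. No passage states that the symptom and adverse-event endpoints will be presented as blinded placebo contrasts, and the synopsis describes a pilot with descriptive statistics by arm. The risk therefore lies in how Section 5.5 would be relied on, not in a declared analysis. The primary endpoint, a gametocyte-load measure, rests on rt-PCR and is little exposed.

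**Conclusion.** The point holds for site staff. Section 5.5 is wrong as written, because Section 3 and the partial-blind label contradict it. Section 3's claim that staff are unaware of the arms other than regular tea is not attainable with these arms: 80 of 96 active participants (83%) have no nominally matched placebo, and the staff who teach and observe their regimens can infer active treatment while also recording symptoms and grading and attributing adverse events.

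This assumes that staff know the arm list and, for TG1, that flavour is perceptible to them. It does not depend on what participants are told. The size is a count of participants without a matched placebo. It is not an estimate of bias, which the documents give no means to quantify. The affected outcomes are symptoms, adverse events and causality. The correction should be made, but it does not threaten the primary endpoint.

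**What to change.** 1. Reconcile the synopsis and Sections 3, 5.5, 6.2 and 6.3 into one statement of who is blind to what, separately for participants, the staff who teach and observe, and the staff who assess outcomes.
2. State that only TG4 versus TG7 has a nominally matched placebo, and that even this comparison is assessor-blind only if observers are not assigned by arm.
3. Report symptom, adverse-event and causality contrasts of TG1, TG2, TG3, TG5 and TG6 with control, and every contrast with TG8, as descriptive and not assessor-blind.

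This is protocol wording and labelling of comparisons. It needs no new arm, no additional participants and no change to any regimen. If the sponsor wants TG4 versus TG7 to be assessor-blind, observer allocation would have to be reorganised with existing staff. The price is a more modest claim about blinding.
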